6.1.1.2 Rabbit anti-thymocyte globulin (r-ATG)

Usually, r-ATG (Thymoglobuline[®]) will be administered at a dose of 2.5 to 3.5 mg/Kg/day on Days 1 to 5 as a slow intravenous infusion per local practice. The exact dose of r-ATG should be decided at the discretion of the investigator but should be within the above range.

Premedication with corticosteroids, acetaminophen, and/or an antihistamine 1 hour prior to each infusion of r-ATG is recommended and may reduce the incidence and intensity of infusion-associated reactions (detailed in [Section 6.2.1](#)). For the treatment for anaphylaxis and infusion-associated reactions, local label should be followed.

6.1.1.3 Cyclosporine (CsA)

CsA (Neoral[®]) will be administered orally every 12 hours from Day 1 at a starting dose of 3-6 mg/Kg/day. Dosing of CsA should be titrated individually to obtain a therapeutic trough level of 150-250 µg/L, recommended to be as close to 200 µg/L as possible in the core treatment part. In the extension part, CsA should last for at least 18 months, if well tolerated, and will be maintained or tapered based at the discretion of the investigator according to local practice in this period. It is recommended that CsA treatment dose will last for at least 3 months after achieving the best hematologic response, and after that CsA will be decreased by 0.3 mg/kg every month or 1mg/kg every 3 months.

For administration of CsA, the local label contraindications should be considered in accordance with exclusion criterion. Certain other medications can change the level of CsA in the blood. Some of these medications are azoles (e.g. ketoconazole, fluconazole, voriconazole), methylprednisolone, erythromycin, diltiazem, rifampin, phenytoin and phenobarbital. The participant must inform the investigator of any medication taken concomitantly while on the study. More frequent CsA serum levels may be obtained as needed to achieve target therapeutic levels and avoid toxicity when participants are taking any medications that may change the CsA level. In terms of concomitant medications requiring caution and/or dose modification, refer to [Section 6.2.1.1](#). Grapefruit and grapefruit juice may increase the effects of CsA by increasing the amount of this medicine in the body. Participants will be advised not to eat grapefruit or drink grapefruit juice while taking this medicine. For detailed information, see [Section 6.7.2](#).

CsA dose may be reduced or interrupted temporarily when clinically indicated at the discretion of the investigator or treating physician (e.g. AE grade 2 or higher). The parenteral route of administration may be used temporarily for CsA administration if indicated. Temporary interruptions for transient toxicities grade 2 or higher or dose adjustments will be reported. Per protocol interruptions and reductions will not be reported as deviations.

6.1.2 Additional study treatments

The investigational site is responsible for sourcing all additional study treatments.

Infection prophylaxis

Prophylactic regimen against infection will be administered at the discretion of the investigator or treatment physician following local guidelines. Infection prophylaxis (antibacterial, antifungal, anti- *Pneumocystis Jirovecii*, and antiviral) will not be routinely administered systematically with the immunosuppressive regimen but may be administered at the discretion

of the investigator or treatment physician on a case by case basis. Prophylactic therapy may be continued at the discretion of the investigator.

Premedications of infusion associated reactions

Premedication with corticosteroids, acetaminophen, and/or an antihistamine prior to each infusion of r-ATG should follow the local label of r-ATG to reduce the incidence and intensity of infusion associated reactions.

Supportive care

Supportive care for the participant (e.g., transfusion support with RBC, platelet or granulocytes, anti-infective care and/or growth factors) will be allowed as clinically indicated, as presented in [Section 6.2.1](#).

6.1.3 Treatment arms/group

This is a single arm study.

6.1.4 Guidelines for continuation of treatment

For participants who meet any criteria for dose interruption described in [Section 6.1.1.1](#), the investigator will follow the guideline presented in [Section 6.1.1.1](#). For participants who meet any toxicity criteria, the investigator will follow the guideline on dose reduction, interruption and/or discontinuation presented in [Section 6.5.1.1](#) and [Section 6.5.1.2](#). Participants can remain on study treatment until toxicity or withdrawal of consent, refer to [Section 6.5.2](#) and [Section 9.1.2](#)

6.1.5 Treatment duration

The core treatment part of this study is 6 month from the start of eltrombopag treatment (Day 1 to Week 26). Participants assessed as responders at Week 26 will be eligible to enter the extension part and may continue treatment with eltrombopag and CsA after Week 26 until Week 52.

Core treatment part

The planned duration of eltrombopag treatment is 6 months in the core treatment part. Participants may be discontinued from treatment earlier due to unacceptable toxicity, disease progression and/or treatment is discontinued at discretion of the investigator or of the participant (see [Section 9.1.1](#)).

The administration of r-ATG will be from Day 1 to Day 5.

For all participants, CsA will be administered at doses that obtain the target trough level range for 6 months if well tolerated. CsA dose may be interrupted temporarily when clinically indicated at the discretion of the investigator or treating physician. The parenteral route of administration may be used temporarily for CsA administration if indicated. Temporary interruptions for transient toxicities or dose adjustments will be reported. Per protocol interruptions will not be reported as deviations.

Extension part

The participants assessed as responders at Week 26 are eligible to enter the extension part. Eltrombopag will be provided up to Week 52 for the participants who enter the extension part and are considered to require continued treatment. For the participants who meet the discontinuation criteria in [Section 9.1.1](#), the study treatment will be discontinued.

In extension part, CsA will last for at least 18 months after Week 26 if well tolerated (total duration is from Day 1 to at least Year 2). CsA will be maintained or tapered based on the discretion of the investigator according to local practice. It is recommended that CsA treatment dose last for at least 3 months after achieving the best hematologic response, and after that CsA is recommended to be tapered by 0.3 mg/kg every month or 1 mg/kg every 3 months. CsA dose may be decreased or interrupted temporarily when clinically indicated at the discretion of the investigator or treating physician. Temporary interruptions for transient toxicities or dose adjustments will be reported. Per protocol interruptions will not be reported as deviations. After Year 2 (Week 104), CsA administration will be at the discretion of the investigator, and will not be provided within the trial anymore.

6.1.5.1 Treatment beyond disease progression

Study treatment beyond disease progression is not applicable for this study because the participant should discontinue the study treatment once assessed as non-responder at Week 26 or relapse at any time, due to the discontinuation criteria in [Section 9.1.1](#). Other treatments can rely on investigator's discretion or refer to treating physician after disease progression.

6.2 Other treatment(s)

6.2.1 Concomitant therapy

All medications (including non-prescription drug and herbal medicines), procedures, and significant non-drug therapies (including physical therapy and blood transfusions) administered after the participant was enrolled into the study (after signing the ICF) must be recorded in the concomitant medications/significant non-drug therapies or procedures pages on the case report forms (CRFs):

- Drug for aplastic anemia other than r-ATG and CsA (G-CSF, iron chelation therapy and supportive therapy except transfusions): from 7 days before the start of administration of the investigational product (or from the screening visit, whichever is earlier) to completion of study;
- RBC and platelet transfusion: from 60 days before the start of administration of the investigational product to the end of eltrombopag treatment for participants who discontinue eltrombopag due to non-response at W26, relapse or alternative SAA treatment, and until the completion of study for all the other participants;
- All concomitant therapy other than the above-mentioned: up to the resolution of the last reported AE.

Transfusions with platelets and/or RBC may be given during study participation as medically necessary per local practice. In general, platelet transfusions should be administered prophylactically when the platelet count $<10 \times 10^9/L$ or when significant bleeding occurs. Prior

to administration of r-ATG, a daily threshold of $20 \times 10^9/\text{L}$ should be used for the duration of the r-ATG course. In participants judged to have additional risk factors for bleeding, a higher prophylactic transfusion threshold of $20 \times 10^9/\text{L}$ is also recommended. Packed RBCs are recommended generally to be administered for hemoglobin $<60 \text{ g/L}$, and it should be individualized according to co-morbidities. Improvement in counts that are dependent upon transfusion will not be considered as fulfilling response criteria in the efficacy assessments (see [Section 8.3](#)).

The use of antibiotics (except for macrolide antibiotics, which may increase the concentration of CsA, mentioned in [Section 6.2.1.1](#)), anti-fungals, and granulocyte colony stimulating factor (G-CSF) are permitted. The local hospital guidelines for treatment of infections / febrile neutropenia should be followed. Cautions should be taken when azole anti-fungals are administered, mentioned in [Section 6.2.1.1](#).

Iron chelation is not allowed during the study until Week 26, unless the participant was taking it before the study treatment started.

Each concomitant drug must be individually assessed against all exclusion criteria/prohibited medication. If in doubt, the investigator should contact the Novartis medical monitor before enrolling a participant or allowing a new medication to be started. If the participant is already enrolled, contact Novartis to determine if the participant should continue participation in the study.

6.2.1.1 Permitted concomitant therapy requiring caution and/or action

Permitted concomitant medications/therapies should be taken/conducted in accordance with the individual product information for dose adjustment and monitoring recommendations and standard practice.

Eltrombopag

If concomitant administration of drugs with a “Known risk of Torsades de Pointes” is required and cannot be avoided, investigational drug must be interrupted. If, based on the investigator assessment and clinical need, study treatment is resumed, close electrocardiogram (ECG) monitoring is advised.

Substrates of BCRP and OATP1B1

Preclinical data showed that eltrombopag is an inhibitor of the transporters OATP1B1 and BCRP, therefore use of concomitant medications that are known substrates for these transporters should be avoided. If they cannot be avoided, caution should be used during concomitant administration with eltrombopag.

In a clinical drug interaction study it showed co-administration of eltrombopag 75 mg once daily for 5 days with a single 10 mg dose of the OATP1B1 and BCRP substrate rosuvastatin increased plasma rosuvastatin Cmax by 2-fold and AUCinf by 55%. Administration of the hydroxy methylglutaryl coenzyme A (HMG-CoA) reductase inhibitor (statins) should be with caution and a 50% dose reduction of statins is recommended during the study, with close monitoring for safety, such as liver chemistry and signs and symptoms of myolysis, and efficacy,

such as cholesterol and triglycerides (refer to individual product information for monitoring recommendations).

Concomitant administration of eltrombopag and other OATP1B1 or BCRP substrates should be used with caution. A list of substrates of BCRP and OATP1B1 is available in Appendix 1 (See [Section 16.1](#)).

Polyvalent Cations (Chelation)

Eltrombopag chelates with polyvalent cations such as aluminum, calcium, iron, magnesium, selenium and zinc. Eltrombopag should be taken at least two hours before or four hours after any products such as antacids, calcium-rich foods (e.g., dairy products and calcium-fortified juices), or mineral supplements containing polyvalent cations to avoid significant reduction in eltrombopag absorption.

Participants requiring routine (e.g. daily) acid suppression should be encouraged to take H2 antagonists or proton pump inhibitors. Participants requiring occasional acid suppression may take liquid or chewable antacids provided eltrombopag is taken at least two hours before or four hours after any consumption of polyvalent cation containing antacids.

Food Interaction

To minimize impact of food in eltrombopag absorption, eltrombopag must be taken at least one hour before or two hours after food containing little (<50 mg) or preferably no calcium. Administration of a single 50 mg-dose of eltrombopag with a standard high-calorie, high-fat breakfast that included dairy products reduced plasma eltrombopag AUC_{inf} by 59% (90% CI: 54%, 64%) and C_{max} by 65% (90% CI: 59%, 70%). Foods low in calcium (defined as <50 mg calcium per serving) including fruit, lean ham, beef and unfortified (no added calcium, magnesium, iron) fruit juice, unfortified soy milk, and unfortified grain did not significantly impact plasma eltrombopag exposure, regardless of calorie and fat content.

Drugs affecting coagulation/bleeding

The following drugs have a possibility that affects the assessment of bleeding. And in the event their use is clinically indicated and cannot be avoided under the discretion of investigator, those drugs will be permitted, but the participant(s) will be excluded from bleeding analyses during the time period the participant was exposed to the medication.

- Drugs that affect platelet function (including but not limited to, aspirin, clopidogrel and/or non-steroidal anti-inflammatory drugs [NSAIDs])
- Anticoagulant (warfarin, heparin, etc.)

R-ATG

Thymoglobulin can stimulate the production of antibodies that cross-react with other rabbit immune globulins, therefore concomitant use of other rabbit immune globulins should be avoided. If they cannot be avoided, cautions should be used during concomitant administration with r-ATG.

CsA

The concomitant use of CsA with the following requires caution:

- Potassium or potassium supplements, potassium-sparing diuretics, angiotensin converting enzyme inhibitors, angiotensin II receptor antagonists which may result in significant increases in serum potassium;
- Medications which may decrease the concentration of CsA: barbiturates, carbamazepine, oxcarbamazepine, phenytoin, nafcillin, sulfadimide, rifampicin, octreotide, probucol, orlistat, hypericum perforatum (St. John's wort), ticlopidine, sulfipurazone, terbinafine, bosetan;
- Medications which may increase the concentration of CsA: macrolide antibiotics (erythromycin, azithromycin, clarithromycin), ketoconazole, fluconazole, itraconazole, voriconazole, diltiazem, nicardipine, verapamil, metoclopramide, oral contraceptives, danazol, methylprednisolone (high dose), allopurinol, amiodarone, cholic acid and derivatives, protease inhibitors, imatinib, colchicine, nefazadone;
- Medications which may exhibit nephrotoxic synergy; aminoglycosides (gentamycin, tobramycin), amphotericin B, ciprofloxacin, vancomycin, trimethoprim (+ sulfamethoxazole), non-steroidal anti-inflammatory drugs (including diclofenac, naproxen, sulidac), melphalan, histamine, H2-receptor antagonists (cimetidine, ranitidine), methotrexate, tacrolimus;
- Concomitant use with nifedipine may result in increased rate of gingival hyperplasia;
- CsA is an inhibitor of CYP3A4 and P-glycoprotein and may increase plasma levels of co-medication that are substrates of this enzyme and/or transporter.
- CsA may reduce the clearance of digoxin, prednisolone, HMG-coA reductase inhibitors (statins), etoposide, aliskiren, bosetan or dabigatran. If co-administration is necessary, close clinical observation is required in order to enable early detection of toxicity. Co-administration of CsA increases blood/plasma concentrations of everolimus, sirolimus, repaglinide, bosetan, aliskiren, dabigatran, and the anthracyclines.

6.2.2 Prohibited medication

Use of the treatments displayed in the below table are not allowed during the study.

Table 6-6 Prohibited medication and therapy

Medication/Therapy	Prohibition period	Action taken
Any other TPO-R agonists (e.g. recombinant humanized thrombopoietin (rhTPO) [TeBiAo], romiplostim [N-plate], Interleukin-11 [Neumega])	During screening, during the administration of study treatment, and when followed as responders.	During screening: considered a screen failure During the administration of study treatment: discontinue study treatment
ATG/ALG other than the study treatment, cyclophosphamide, alemtuzumab		When participants are followed as responders off study treatment: discontinue from efficacy follow-up. Only survival and clonal evolution will be followed then.
Initiation of additional IST other than corticosteroids or CsA		
Anabolic steroids		
HSCT		

Medication/Therapy	Prohibition period	Action taken
The medications which are prohibited in the product label of r-ATG or CsA	During the administration of r-ATG or CsA	Discontinue study treatment

Following IST, any vaccinations, including influenza, should be avoided as there is a theoretical risk of disease relapse ([Killick et al 2016](#)).

There is no definite contraindication for the use of an inactivated, viral-vector, or mRNA based SARS-CoV-2 vaccine in subjects treated with eltrombopag. Recognizing that multiple vaccines may have various mechanisms of action with different associated potential risks, the decision of vaccination for SARS-CoV-2 should be done on a case-by-case basis and at the discretion of the investigator. The administered vaccine must be recorded as a concomitant medication.

The local labels should be considered in regard to contraindicated drugs during r-ATG/CsA administration.

Participants must abstain from using herbal supplements, investigational drugs or not marketed drugs without a well-known safety profile and from using prohibited prescription or nonprescription drugs within 7 days or 5-half-lives (whichever is longer) prior to the first dose of study treatment and until completion of follow-up procedures unless, in the opinion of the Investigator and Sponsor, the medication will not interfere with the study.

6.3 Participant numbering, treatment assignment, randomization

6.3.1 Participant numbering

Each participant is identified in the study by a Participant Number (Participant No.), that is assigned when the participant is first enrolled for screening and is retained as the primary identifier for the participant throughout his/her entire participation in the trial. The Participant No. consists of the Center Number (Center No.) (as assigned by Novartis to the investigative site) with a sequential participant number suffixed to it, so that each participant is numbered uniquely across the entire database. Upon signing the informed consent form, the participant is assigned to the next sequential Participant No. available.

The investigator or designated site staff will contact the Interactive Response Technology (IRT) and provide the requested identifying information for the patient to register them into the IRT. Once assigned, the Participant No. must not be reused for any other participant and the Participant No. for that individual must not be changed.

6.3.2 Treatment assignment, randomization

This is a single arm, non-randomized study. No randomization will be performed in this study. Upon completion of all the required screening assessments, eligible participants will start study treatment at Day 1.

6.4 Treatment blinding

This is a single arm, open label study.

6.5 Dose escalation and dose modification

6.5.1 Dose modifications

The eltrombopag dose adjustment based on treatment response are in [Section 6.1.1.1](#).

For participants who do not tolerate the protocol-specified dosing schedule, dose interruptions, and/or reductions are either recommended or mandated in order to allow participants to continue the study treatment. Deviations to mandatory dose interruptions and/or reductions are not allowed.

Permanent treatment discontinuation is mandatory for specific events indicated as such in [Section 9.1.1](#).

These dose changes must be recorded on the Dosage Administration Record – electronic case report form (eCRF).

6.5.1.1 Dose adjustments for QTcF prolongation

In case of QTcF >500 msec, (or QTcF prolongation >60 msec from baseline)

Confirm readout:

1. Assess the quality of the ECG recording and the QT value and repeat if needed
2. Interrupt eltrombopag only if no other cause has been identified and if there are cardiac signs and symptoms
3. Determine the serum electrolyte levels (in particular hypokalemia, hypomagnesemia). If abnormal, correct abnormalities before resuming investigational drug treatment
4. Review concomitant medication associated with QT prolongation, including drugs with a “Known”, “Possible”, or “Conditional risk of Torsades de Pointes” (crediblemeds.org), and drugs with the potential to increase the risk of investigational drug exposure related QT prolongation
5. Check investigational drug dosing schedule and treatment compliance
6. Consider collecting a ECG time-matched PK sample as unscheduled PK sample, and record time and date of last investigational drug intake
7. Repeat ECG and confirm ECG diagnosis by a cardiologist

After confirming ECG reading at site, if QTcF > 500 msec

- Interrupt eltrombopag
- Correct electrolytes, eliminate culprit concomitant treatments, and identify and address clinical conditions that could potentially prolong the QT
- Consult with a cardiologist (or qualified specialist)
- Increase cardiac monitoring as indicated, until the QTcF returns to ≤ 480 msec
- Dose can be resumed if QTc reduces or an alternate cause has been identified and if there are no cardiac signs and symptoms

If resolved (QTcF ≤ 480 msec), consider re-introducing treatment at reduced dose, and increase ECG monitoring for the next treatment(s):

- If QTcF remains \leq 500 msec after dose reduction, continue planned ECG monitoring during subsequent treatment
- If QTcF recurs $>$ 500 msec after dose reduction, discontinue participant from study treatment.

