Additional, unscheduled, safety ECGs may be repeated at the discretion of the investigator at any time during the study as clinically indicated. For any ECGs with participant safety concerns, two additional ECGs must be performed to confirm the safety finding. Unscheduled ECGs with clinically significant findings should be collected in triplicate. The individual ECGs should be recorded approximately 2 minutes apart. Local cardiologist ECG assessment may also be performed at any time during the study at the discretion of the investigator. A monitoring or review process should be in place for clinically significant ECG findings throughout the study and especially at baseline before administration of study treatment.

Clinically significant abnormalities must be recorded on the CRF as either medical history/current medical conditions or AEs as appropriate. Clinically significant findings must be discussed with Novartis prior to enrolling the participant in the study. New or worsened clinically significant findings occurring after informed consent must be recorded as AEs.

In the event that a QTcF value of > 500 ms is observed or if an unscheduled ECG is performed for safety reasons, it is recommended to collect a ECG time-matched PK sample as unscheduled PK sample and record the time and date of the last investigational drug intake to determine the drug exposure. Dose adjustments in case of QT prolongation should be performed per [Section 6.5.1.1](#).

Paper ECGs should be appropriately labeled and kept in the source documents at the study site. If an unscheduled ECG is performed at an external medical facility, a copy of the ECG should be obtained and kept in the source documents at the study site.

8.4.2.1 **Cardiac imaging - echocardiogram**

An echocardiogram scan is required to be completed at screening. Clinically significant abnormalities present when the participant signed the informed consent should be reported as Medical History on the appropriate eCRF. New or worsened clinically significant findings occurring after informed consent must be recorded as an AEs on the eCRF.

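### Protocol 6.5.1.1 gives two restart statements after a confirmed QTcF above 500 msec that do not agree, and which one is followed can decide whether a stopping rule applies

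*Protocol*

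**What the plan says.** Protocol Section 6.5.1.1 has three consecutive blocks.

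- **Confirming the reading.** The trigger is "In case of QTcF >500 msec, (or QTcF prolongation >60 msec from baseline"). Seven numbered steps follow. Step 2 is "Interrupt eltrombopag only if no other cause has been identified and if there are cardiac signs and symptoms". Steps 3 to 5 check electrolytes, concomitant drugs, and dosing and compliance. Step 7 repeats the ECG and has a cardiologist confirm it.
- **After confirmation.** This block opens "After confirming ECG reading at site, if QTcF > 500 msec". Its first bullet interrupts eltrombopag and attaches no condition. A later bullet steps up cardiac monitoring until QTcF is back to 480 msec or lower. The last bullet is "Dose can be resumed if QTc reduces or an alternate cause has been identified and if there are no cardiac signs and symptoms".
- **Re-introduction.** The next sentence begins "If resolved (QTcF ≤ 480 msec), consider re-introducing treatment at reduced dose". Two sub-bullets follow. If QTcF stays at or below 500 msec after the reduction, planned monitoring continues. If it goes above 500 msec again after the reduction, the participant is discontinued from study treatment.

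Section 6.5.1 adds: "Deviations to mandatory dose interruptions and/or reductions are not allowed". Section 9.1.1 lists meeting a stopping criterion of Section 6.5.1 among the circumstances in which study treatment must be discontinued. The ECG section (8.4.2) does not settle the matter. It says "Dose adjustments in case of QT prolongation should be performed per" Section 6.5.1.1. Neither SAP contains a rule on it.

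**The concern.** Both restart statements concern the same participant, one whose QTcF above 500 msec has been confirmed and whose eltrombopag has been interrupted. Splitting the section into before and after confirmation therefore cannot separate them. They differ on the QTcF value that permits restart, on whether an alternate cause is enough, on whether symptoms matter, and on whether a dose level is given.

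The same ECG could be handled differently at two sites, each following the text. The difference also carries forward. The discontinuation rule presupposes a dose reduction, and only one of the two statements mentions one. The issue is participant safety and consistent handling across sites. It also bears on how cases are classified in the deviation and dose-adjustment summaries (Sections 2.3.1 and 2.4.1 of both SAPs). No efficacy estimate is involved.

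**Working it through.** No sample-size or error-rate figure bears on this, so the check compares the statements as written.

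**1. The restart statements side by side**

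| Feature | A: last bullet after confirmation | B: re-introduction sentence |
|---|---|---|
| QTcF condition | a fall of any size | 480 msec or lower |
| Alternate cause | sufficient without a fall | not mentioned |
| Cardiac signs and symptoms | must be absent | not mentioned |
| Dose level | not stated | reduced |
| Force | permissive (can) | advisory (consider) |

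**2. How often they differ on whether restart is open.** Take three QTcF states (480 or lower; lower than before but above 480; not lower), alternate cause yes or no, and symptoms yes or no: 3 × 2 × 2 = 12 logical cases. These are combinations, not participants.

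- B is met in 1 × 2 × 2 = 4.
- A, with the symptom condition covering both routes: 2 (480 or lower) + 2 (lower but above 480) + 1 (not lower, alternate cause) = 5. A and B share 2, so they differ in (5 − 2) + (4 − 2) = 5 of 12.
- A, with the symptom condition covering only the alternate-cause route: 4 + 4 + 1 = 9. They share 4, so they differ in (9 − 4) + (4 − 4) = 5 of 12.

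The count is 5 of 12 under either grammar of A. It assumes that B is the only condition for restart under its own sentence. Where both are met, only B gives a dose level.

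**3. Example.** A confirmed QTcF falls from 510 to 495 msec without symptoms. A is met, because 495 is below 510. B is not met, because 495 is above 480.

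**4. Link to the stopping rule.** Suppose QTcF later returns to 510 msec.

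- Restarted under B at a reduced dose: this is recurrence above 500 msec after a reduction. The rule in 6.5.1.1 applies, and Section 9.1.1 makes it binding.
- Restarted under A with no reduction, which A does not ask for: the rule's wording is not met, because no reduction preceded the recurrence.

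**5. Step 2 against the post-confirmation interruption.** For a confirmed QTcF above 500 msec there are 2 × 2 = 4 cases (other cause yes or no, symptoms yes or no). Step 2 allows interruption in 1, and the later bullet calls for it in 4. If step 2 still applied after confirmation, they would differ in 3 of 4. If step 2 ends at confirmation, there is no conflict. The text does not expressly say which. Step 2 also turns on whether another cause has been found, yet the checks for causes come in steps 3 to 5.

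**6. The 60 msec trigger.** A rise from 430 to 495 msec is 495 − 430 = 65 msec, above 60, with QTcF still at or below 500. Steps 1 to 7 apply. The post-confirmation block is limited to values above 500 msec, so nothing follows once this rise is confirmed.

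**The case against.** The best case on the other side is that this is a staged procedure read too literally.

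- **Interruption.** A reader might infer that the section flatly contradicts itself on when to interrupt. The block headings do not support that. Step 2 sits under the confirmation heading and the unconditional bullet under the post-confirmation heading. The natural reading is that step 2 lapses on confirmation. This largely stands, and leaves only a missing express limit on step 2.
- **Force of B.** A reader might infer that B forbids restart above 480 msec and demands a reduced dose. It says to consider re-introduction, and forbids nothing in terms. This stands, and it is why the 5 of 12 rests on an assumption. But if B does not limit restart, the 480 msec value has no clear role beside A.
- **Dose under A.** A reader might infer that A authorises resumption at the full dose. It is silent on dose, and B can be read as completing it, with the fall in QTc understood as a fall to the 480 msec named in the monitoring bullet. That is a possible harmonisation, but the text does not state it. It also leaves the alternate-cause route and the differing symptom conditions unexplained.
- **The 60 msec rise.** A reader might infer that this trigger has no action attached. It has all seven steps, and Section 6.1.1.1 allows interruption at the investigator's discretion. Only the instruction after confirmation is missing.
- **Mandatory status.** A reader might infer from Section 6.5.1 that a site cannot tell what is mandatory. That goes too far. The unqualified imperative is the interruption after confirmation, while both restart statements are permissive or advisory.
- **Timing.** Amendment 3 reports all 36 participants enrolled as of 07-Dec-2021. Adding up to 30 days of screening and 52 weeks of eltrombopag gives about early January 2023. Rewording can change little about dosing in this trial. This stands.

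**Conclusion.** The concern holds for the restart wording. After a confirmed QTcF above 500 msec, Section 6.5.1.1 offers two restart statements that differ on threshold, alternate cause, symptoms and dose level, and no other section resolves them. The choice matters because the discontinuation rule is reached only through a dose reduction, which one of the statements never mentions. Section 9.1.1 has other grounds for stopping, such as an unacceptable adverse event or the investigator's judgement, so losing this rule does not remove every route to discontinuation.

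The scope of step 2 and the confirmed 60 msec rise are secondary points of clarity.

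On size: the documents do not say how many participants had a QTcF above 500 msec, and no endpoint, analysis set or statistical figure is affected. The value of correcting the text lies mainly in consistent classification of cases already observed and in any reuse of the section. The conclusion rests on reading the statements as written and takes no view on which clinical rule is right.

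**What to change.** The sponsor should, within Section 6.5.1.1:

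1. reconcile the two restart statements with each other on QTcF value, alternate cause, symptoms and dose level;
2. align the discontinuation wording with the reconciled restart text, so that it is clear whether recurrence counts when no reduction was made;
3. state whether step 2 applies only before confirmation;
4. state what follows a confirmed rise above 60 msec when QTcF is at or below 500 msec.

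The content of each rule is for the sponsor's clinical and safety staff. The cost is wording in one protocol section, with no change to data collection, analyses or sample size. If the protocol is not amended again, a short note in the study report on how any such cases were handled and classified would serve the same purpose for this trial.
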